6.2 Discussion of Study Design

The safety assessments used in this study are recognized and validated standards of measurement.

Bupropion SR is used as an active control in this trial as it is one of the two components in AXS-05. The 3-day up-titration period for AXS-05 and bupropion SR used in this trial is meant to minimize AEs resulting in early drop-outs. This up-titration from QD to BID dosing is consistent with the label for Wellbutrin SR which recommends at least 3 days before up-titrating to BID dosing. No down-titration has been included consistent with the product label for Wellbutrin SR.

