10.1.5 Treatment-Emergent Adverse Events

An AE is defined as treatment emergent if the first onset or worsening is after the first administration of the study drug and not more than 30 days after the last study visit.

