10.2 Management of Adverse Events

Adverse events will be collected from the time of signing the ICF through 30 days after the last study visit or Early Termination, whichever occurs first. Only Serious adverse events will be collected for subjects who screen fail.

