12.1.1 Safety Endpoints

Safety endpoints include the following:

- Adverse Events (AE)
- Adverse Dropouts (ADOs)
- Incidence of Treatment Emergent Adverse Events (TEAEs)
- Clinical laboratory test results
- Vital sign measurements
- Physical examination findings
- Columbia Suicide Severity Rating Scale (C-SSRS)

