12.4.3.1 Adverse Events

Adverse events will be coded by system organ class (SOC) and preferred term using the Medical Dictionary for Regulatory Activities reporting system. Treatment-emergent AEs are defined as any of the following:

- Non-serious AEs with onset on the date of first dose of treatment with the study drug through follow up (7 days after the last dose of study drug);
- Serious AEs with onset on the date of first dose of treatment with the study drug through 30 days after the last dose of study drug;

The number and percentage of subjects with TEAEs will be displayed for each treatment group by SOC and preferred term. Additionally, TEAEs will be tabulated for each treatment group by severity and by relationship to the study drug. A listing of SAEs will be provided if applicable.

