#### **10.2** ADVERSE EVENTS

Each AE and SAE term recorded on the case report forms (CRFs) by primary system organ class (SOC) will be mapped to a preferred term using the MedDRA dictionary. The investigator will assess AE severity and relationship to the study treatment.

A treatment emergent adverse event (TEAE) is defined as any AE with an onset date on or after date of randomization, or any ongoing event on the date of first dose that worsens in severity after date of randomization. Only non-serious TEAEs with an onset date prior to date of last dose and serious TEAEs

AXSOME Therapeutics, Inc. AXS-05-MDD-201 SAP CONFIDENTIAL Page 13 of 16 Version 1.0—11 December 2018

with an onset date prior to date of the final visit + 30 days will be tabulated in summary tables. However, all AEs recorded will be listed. For the purpose calculating treatment emergence and inclusion in summary tables, incomplete onset dates will be imputed as detailed in Appendix A.

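### SAP 10.2 leaves non-serious events that start on the last-dose day or in the next 7 days out of the TEAE tables, matching neither protocol definition

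*SAP*

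**What the plan says.** SAP 10.2 defines a treatment-emergent event as "any AE with an onset date on or after date of randomization", or an event ongoing at first dose that later worsens. The definition has no end date. A separate sentence limits the summary tables: "Only non-serious TEAEs with an onset date prior to date of last dose" are tabulated, together with serious events that start before the final visit plus 30 days. The section adds "However, all AEs recorded will be listed". Neither SAP 10.2 nor SAP 6.3 (changes to planned analyses) explains the cut at last dose.

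The protocol has two definitions of its own:

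- **Protocol 12.4.3.1** counts non-serious events from the date of first dose "through follow up (7 days after the last dose of study drug", and serious events to 30 days after last dose. It then says that TEAEs are displayed by arm, system organ class (SOC) and preferred term.
- **Protocol 10.1.5** makes no split by seriousness. It counts onset or worsening after first dose and "not more than 30 days after the last study visit".

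Protocol 10.2 collects adverse events "through 30 days after the last study visit or Early Termination, whichever occurs first". Visit 9, the telephone call one week after last dose, also records them. Protocol 12.1.1 lists "Incidence of Treatment Emergent Adverse Events (TEAEs") as a safety endpoint.

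**The concern.** The SAP's restriction is a strict inequality, so it removes the last-dose day as well as everything after it. A reaction to the final tablet would not be tabulated if it is non-serious. The week that Visit 9 exists to cover would add nothing to the non-serious tables. On stopping, Protocol 6.2 says: "No down-titration has been included consistent with the product label for Wellbutrin SR". Any non-serious event that first appears after drug is stopped therefore falls wholly in the omitted days.

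Visit 8/Early Termination is affected too. Unused drug is collected there and none is dispensed, so last dose is on or before that visit. A non-serious event dated to that visit is then never tabulated. This visit has the only scheduled post-baseline laboratory tests and physical examination. Laboratory values still reach the shift tables (SAP 10.3). Physical findings are summarized only at Screening (SAP 10.5), so a new finding at Visit 8 would appear only in a listing.

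At stake is whether the by-arm incidence tables are complete for the protocol's single objective (Protocol 5).

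A smaller, separate point runs the other way. The SAP opens the window at randomization (Day 0), but first dose is on Day 1 (Schedule of Assessments, footnote h). Events before any drug was taken can therefore count as treatment-emergent.

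**Working it through.** The plan states no figure to reproduce here. The check is a comparison of windows and a count of onset days.

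**Inputs.** First dose is Day 1 and a completer's last dose is Day 42 (Protocol 6.1). Visit 9 is Day 49 (Protocol 17.2). Let L be the last-dose day.

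**Non-serious events, SAP 10.2 against Protocol 12.4.3.1.**

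- Protocol window: Days 1 to L + 7, which is L + 7 days.
- SAP tabulated days from first dose: Days 1 to L − 1, which is L − 1 days.
- Omitted: (L + 7) − (L − 1) = 8 days, whatever L is.

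| Last dose (L) | SAP days | Protocol days | Omitted | Share |
|---|---|---|---|---|
| Day 42 | 41 | 49 | 8 | 16.3% |
| Day 28 | 27 | 35 | 8 | 22.9% |
| Day 14 | 13 | 21 | 8 | 38.1% |
| Day 7 | 6 | 14 | 8 | 57.1% |
| Day 3 | 2 | 10 | 8 | 80.0% |
| Day 1 | 0 | 8 | 8 | 100% |

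In the last row, a subject who takes only the Day 1 dose has no non-serious event tabulated from Day 1 onward. Only a Day 0 event, before any drug, could be counted.

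If all 60 planned subjects complete, 60 × 8 = 480 of 60 × 49 = 2,940 subject-days are omitted (16.3%).

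**Against Protocol 10.1.5, completer.** The window ends on Day 49 + 30 = Day 79. The SAP counts 41 days, so 79 − 41 = 38 are omitted, and 38/79 = 48.1%. Of these, 8 (Days 42 to 49) fall within scheduled contacts and 30 (Days 50 to 79) come after the last one.

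**Effect on a tabulated rate.** At 30 per arm, one subject whose only event under a preferred term falls in the omitted days lowers that arm's rate by 1/30 = 3.3 percentage points. At an assumed 40 per arm it is 1/40 = 2.5 points.

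**Serious events, completer.** The SAP counts onsets before Day 49 + 30 = Day 79, so through Day 78. Protocol 12.4.3.1 runs to Day 42 + 30 = Day 72. The SAP end point loses nothing against 12.4.3.1 here.

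**Appendix A.** Suppose randomization on 31 August, first dose on 1 September, and an event dated September with no day. The month is not the randomization month, and it is neither before nor after the first-dose month. No listed branch applies, so the default sets onset to 31 August (Day 0). Under the current SAP that event still counts as treatment-emergent. If the window start moves to first dose and the anchor stays, it becomes pre-treatment. The same happens to every event whose onset date is completely missing.

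**The case against.** The strict cut and the mismatch are not in dispute. The case on the other side is about consequence, and several parts of it stand.

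- **The protocol leaves analysis detail to the SAP, and no formal safety comparison is planned.** True, so no test or decision rule changes. But the protocol itself states the TEAE window, and an unexplained narrower one is a discrepancy rather than added detail.
- **The events are visible elsewhere.** All events are listed. Disposition tables show reasons for discontinuation by arm, and adverse dropouts are a separate endpoint. Events that start before last dose and lead to stopping are still tabulated, and C-SSRS data from Visit 9 are kept. None of this gives by-arm incidence by SOC and preferred term for the omitted events.
- **Shares of days are not shares of events.** This stands. The high percentages belong to illustrative early stoppers, and most of the 48% lies after the last scheduled contact.
- **Thirty per arm is not the safety denominator.** This stands. Thirty is the target for compliant completers (Protocol 12.2) or for independently confirmed subjects (SAP 9.5). The safety population takes in everyone who received study medication, so 3.3 points is an upper bound if the safety arms are larger.
- **The absence of down-titration does not predict events after stopping.** Correct. It shows only where such events would fall.
- **The start-date problem is about one day and over-counts.** Correct. Appendix A does no harm until the start is moved, which is why the two edits must go together.
- **The proposed window is another hybrid.** Partly fair. Section 12.4.3.1 is preferred for non-serious events because it governs the SOC and preferred-term display and ends at Visit 9, the last scheduled enquiry about adverse events.

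**Conclusion.** The concern holds. Followed as written, SAP 10.2 under-counts a listed endpoint for the protocol's only objective. Against Protocol 12.4.3.1 it drops 8 onset days per subject, which is 16% of a completer's window and a larger share the earlier a subject stops. The day counts assume first dose on Day 1 and, for completers, last dose on Day 42 and the last visit on Day 49.

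The number of events lost, and any difference between arms, cannot be estimated because the documents give no event rates or onset distribution. The finding is incomplete tabulation, not demonstrated bias. It should be corrected before database lock.

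**What to change.** 1. In SAP 10.2, tabulate non-serious events with onset or worsening from first dose through 7 days after last dose, and start treatment emergence at first dose. Worsening is already in the SAP and in Protocol 10.1.5, though 12.4.3.1 does not mention it.
2. In the adverse event part of Appendix A, replace every randomization anchor with first dose in the same edit, so that missing or partial onset dates are not classed as pre-treatment.
3. Keep the SAP's serious-event end point of final visit plus 30 days.
4. State in the SAP that Protocol 10.1.5 and 12.4.3.1 give conflicting windows that must be reconciled, and say which one each table follows.

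The cost is a SAP text edit and a small change to the TEAE and date-imputation programs. No new data are needed, because Visit 9 already records adverse events. Tabulated non-serious counts may rise slightly, and Day 0 onsets will drop out. If the sponsor also corrects the protocol text, Protocol 13.7 requires a formal amendment.

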## **10.3** LABORATORY ASSESSMENTS

Chemistry and Hematology, Urinalysis and Coagulation Profile will be assessed at Screening and Week 6. Summary statistics for these parameters will be presented by visit for the actual value and change from baseline for each test in each laboratory category (Hematology, Chemistry, Urinalysis, and Coagulation Profile). Shift tables will be presented for shifts from baseline lab categories to end of study laboratory category. The three laboratory categories will be: L (below lower bound of normal range), N (within normal range), and H (above higher bound of normal range).

If a lab value is reported using a non-numeric qualifier (e.g., less than ( $\leq$ ) a certain value, or greater than (>) a certain value), the given numeric value will be used in the summary statistics, ignoring the non-numeric qualifier.

If a subject has repeated laboratory values for a given time point, the value from the first evaluation at that time point will be used for summarization purposes. For the purpose of determining baseline, the last nonmissing observation on or prior to randomization will be used. The Week 6 values will be the last post-baseline value on or prior to Week 6.

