9.1 Study Periods, Visits, and Procedures

9.1.1 Visit 1, Screening (Days –28 to –1)

Subjects will be screened within 28 days before randomization in the study. The following procedures will be performed at Screening:

- Provide the subject with the informed consent document and explain the rationale for the study, providing ample time for participants and authorized representatives to ask questions. Consent will be obtained before any subsequent screening related procedures are performed.
- Review inclusion/exclusion criteria.
- Review and record: Patient medical/psychiatric history and demographics.
- Review and record: Medications currently being taken or taken within the previous 1 year (5 years in the case of psychiatric drug history) of Screening (including OTC medications, vitamins, and supplements). Determine medication washout requirements and duration. Subjects who are receiving prohibited medications (e.g., antipsychotics, antidepressants, anticonvulsants/mood stabilizers, anxiolytics, and sedatives/hypnotics) except as specifically allowed, will require a washout period. All prohibited medications should be washed out before Visit 2.
- Perform a complete physical examination (excluding breast and genitourinary examination) with review of body systems.
- Record vital signs: Blood pressure, pulse, respiratory rate, and oral temperature after subject has been seated for 5 minutes.
- Measure height and weight.
- Collect blood and urine samples for central clinical laboratory tests (hematology, serum chemistry, urinalysis, thyroid panel, and serum ethanol); see Section 9.3.3.2.1 for a complete list of required laboratory tests.
- Collect urine for an on-site urine drug screen and urine pregnancy test (if female).
- Conduct SCID-5-CT interview to confirm MDD diagnosis.
- Administer evaluations:
 - MADRS (≥ 25 inclusive)
 - CGI-S (\geq 4 inclusive)
 - o QIDS-SR-16
 - Columbia Suicide Severity Rating Scale (C-SSRS) (lifetime)

•

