9.3.3.2 Clinical Laboratory Safety Assessments

9.3.3.2.1 Clinical Laboratory Tests to Be Performed

Samples for the following laboratory tests will be collected at the time points specified in the Schedule of Assessments (Section 17.2).

Hematology	Hemoglobin, hematocrit, red blood cell count, red blood cell indices (mean corpuscular volume, mean corpuscular hemoglobin, mean corpuscular hemoglobin concentration), platelet count (or estimate), and white blood cell count (including differential), absolute and % Neutrophil, Lymphocyte, Basophil, Monocyte, and Eosinophils
Serum Chemistry	Albumin, total bilirubin, direct bilirubin, total protein, calcium, alkaline phosphatase, alanine aminotransferase, aspartate aminotransferase, blood urea nitrogen, creatinine, random glucose, sodium, potassium, chloride, C-reactive protein (CRP), cholesterol
Urinalysis	pH, specific gravity, blood, glucose, protein, ketones, and leukocyte esterase
Thyroid Panel	TSH, Free T3, Free T4
Urine Drug Screen	Benzoylecgonine (cocaine), barbiturates, amphetamines, benzodiazepines, cannabinoids, opiates, methadone, phencyclidine, ecstasy (MDMA)
Serum Ethanol Level	
Repeat Urine Drug Screen	May be performed at random during the study upon request of the investigator
Repeat Serum Ethanol Level	May be performed at random during the study upon request of the investigator

Other laboratory assessments may be repeated at any visit if there was an abnormal finding at the most recent previous evaluation or if additional information is clinically necessary to appropriately follow up and/or manage an adverse experience.

All blood and urine samples will be sent to a central laboratory for analyses.

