12.4.3.2 Clinical Laboratory Evaluations

For continuous laboratory parameters, descriptive statistics will be presented for each visit and for the changes from Baseline to each subsequent visit by treatment group.

Additionally, clinical laboratory parameters will be categorized as low, normal, or high according to laboratory range specifications and the number and percentage of subjects in each category will be presented in shift tables.

Laboratory values that are outside the normal range will also be flagged in the data listings, along with corresponding normal ranges.

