17.2 Schedule of Assessments

Visit	Screening Visit 1	Baseline Visit 2	Phone Call Visit 3	Visit 4	Visit 5	Visit 6	Visit 7	Visit 8 / ET	Visit 9 Follow-up ^a
Study Day	-28 to -1	0	3 (+1)	7 (±2)	14 (±2)	21 (±2)	28 (±2)	42 (±2)	49 (±2)
Week	-4 to -1			Week 1	Week 2	Week 3	Week 4	Week 6	Week 7
Informed Consent	X ^b								
Inclusion/Exclusion Criteria	Х	Х							
Demographics	Х								
Medical/Psychiatric History	Х								
Medication History	Х								
Physical Examination	Х							Х	
Vital Signs, Height/Weight ^c	Х	Х		Х	Х	Х	Х	Х	
Laboratory Tests ^d	Х							Х	
Urine Drug Screen ^e	Х	Х						Х	
Serum Ethanol ^e	Х							Х	
Urine Pregnancy Test (all female subjects)	Х	Х						Х	
SCID-5-CT	Х								
MADRS	Х	Х		Х	Х	Х	Х	Х	
QIDS-SR-16	Х	Х		Х	Х	Х	Х	Х	
CGI-S (Severity)	Х	Х		Х	Х	Х	Х	Х	
CGI-I (Improvement)				Х	Х	Х	Х	Х	
C-SSRS	Х	Х		Х	Х	Х	Х	Х	Х
Randomization		Х							
Instruct to begin BID dosing			Х						
Study Drug Dispensation ^h		Х		Х	Х	Х	Х		
Study Drug Accountability			Х	Х	Х	Х	Х	Х	
Prior and Concomitant Medications	Х	Х	Х	Х	Х	Х	Х	Х	Х
Adverse Events	Х	Х	Х	Х	Х	Х	Х	Х	Х

Abbreviations: SCID-5-CT = Structured Clinical Interview for Diagnostic and Statistical Manual of Mental Disorders, Fifth Edition, Clinical Trials Version; ET = early termination; EOS = End of Study; MADRS = Montgomery-Åsberg Depression Rating Scale; QIDS-SR-16 = Quick Inventory of Depressive Symptomatology-Self- Rated; CGI-I = Clinical Global Impressions–Improvement; CGI-S = Clinical Global Impressions–Severity; C-SSRS = Columbia - Suicide Severity Rating Scale;

a Safety follow-up visit to be performed telephonically.

b Informed consent must be signed prior to any study procedures being performed.

c Vital signs, including blood pressure, heart rate, respiratory rate, and oral body temperature, will be measured after the subject has been in a seated position for at least 5 minutes. Height will be measured at Visit 1 and weight at Visit 1 and Visit 8 (EOS or ET).

d Clinical laboratory tests will include hematology, serum chemistry, urinalysis and thyroid panel.

e May be performed at other study visits per investigator judgment. Subjects with positive urine drug screen or serum ethanol levels at Visit 1 may be allowed in study depending on circumstances described to the Medical Monitor and a negative repeat UDS is obtained before Visit 2.

f

h Subjects will begin to take study drug the morning of Day 1 (morning after Visit 2).

APPENDICES

- B. Regulations and Good Clinical Practice Guidelines

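### SAP 10.3 tabulates a coagulation profile that the protocol never collects and leaves out the thyroid panel that it does collect

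*SAP*

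**What the plan says.** SAP 10.3 lists its laboratory groups twice. The first sentence gives what is measured and when: "Chemistry and Hematology, Urinalysis and Coagulation Profile will be assessed at Screening and Week 6". The next sets the scope of the summary statistics: "for each test in each laboratory category (Hematology, Chemistry, Urinalysis, and Coagulation Profile". Shift tables from baseline to end of study follow. That sentence names no panel, so its scope comes from the same list. Thyroid tests appear nowhere in the section.

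The protocol describes a different fourth panel. Footnote d of the schedule (17.2) reads: "Clinical laboratory tests will include hematology, serum chemistry, urinalysis and thyroid panel". The test table in 9.3.3.2.1 gives the thyroid panel its own row, separate from serum chemistry, with the content "TSH, Free T3, Free T4". The Screening procedures (9.1.1) say: "Collect blood and urine samples for central clinical laboratory tests (hematology, serum chemistry, urinalysis, thyroid panel, and serum ethanol"; the Visit 8/ET procedures (9.1.5) repeat this.

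For analysis, Protocol 12.4.3.2 says of continuous laboratory parameters that "descriptive statistics will be presented for each visit and for the changes from Baseline to each subsequent visit", by treatment group, and adds low/normal/high shift tables.

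On repeated samples, SAP 10.3 says that "the value from the first evaluation at that time point will be used for summarization purposes", and later: "The Week 6 values will be the last post-baseline value on or prior to Week 6".

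**The concern.** Safety and tolerability are the protocol's only stated objective (section 5), and laboratory results are a listed safety endpoint (12.1.1). SAP 3.0 makes the approved SAP the basis for every analysis in the study report, so a programmer working from SAP 10.3 builds a coagulation table with nothing to fill it and has no instruction to build a thyroid table.

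Thyroid is not an idle panel here. Exclusion 23 admits subjects with stabilised thyroid disease whose TSH lies above 0.75 × LLN and below 1.25 × ULN, so some may enter outside the reference range. A baseline-to-end shift table by arm is the display that would show whether such values moved.

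**Working it through.** There is no plan figure to reproduce. The check is a comparison of lists, followed by a count.

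**1. Lists side by side**

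| Laboratory group | Protocol 9.3.3.2.1 and 17.2 footnote d | Drawn at | SAP 10.3 |
|---|---|---|---|
| Hematology | yes | Visit 1, Visit 8/ET | yes |
| Serum chemistry | yes | Visit 1, Visit 8/ET | yes |
| Urinalysis | yes | Visit 1, Visit 8/ET | yes |
| Thyroid panel | yes, own row | Visit 1, Visit 8/ET | no |
| Coagulation profile | no | never | yes, twice |

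Three groups match. One is in the SAP but not collected, and one is collected but not in the SAP. The nearest protocol item to coagulation is the platelet count, which sits under hematology.

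**2. Could the thyroid tables be made?** Yes. SAP 10.3 takes the last non-missing value on or before randomization as the laboratory baseline, so the Screening sample serves. Visit 8/ET supplies the post-baseline value.

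**3. Size**
- Analytes: 3 (9.3.3.2.1). Post-baseline draws: 1 (Visit 8/ET). Subjects: about 60 assumed, from Protocol 12.2.
- Post-baseline values: 3 × 60 × 1 = 180.
- Including Screening: 3 × 60 × 2 = 360, of which 180 are pre-treatment.

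The 60 is a target for compliant completers, not the Safety Population used for laboratory tables. Each further treated subject with a Visit 8/ET sample adds 3 post-baseline values; each subject without one adds none.

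**4. Repeat samples.** The first-evaluation sentence settles repeats within a time point. The Week 6 sentence decides which post-baseline sample stands for the end of study, and so carries an early-termination sample into the shift table. Taking Week 6 as Day 42:
- Sample on Day 42, retest later: both sentences give the Day 42 value, because the retest falls after Week 6.
- Sample on Day 40, retest by Day 42: the first-evaluation sentence gives Day 40, and the last-value sentence gives the retest.
- ET sample retested before Day 42: the two can again differ.
- Visit 8 sample on Day 43 or 44: inside the schedule's window (42 ± 2 = Days 40 to 44), but after Week 6 if that means Day 42, so it may not count at all.

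**5. Vital signs.** Protocol 12.4.3.3 includes oral temperature among the summaries. SAP 10.4 does not list it.

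**The case against.** The best case on the other side is that this is a labelling slip with little consequence. Several parts of it stand.

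- **The values survive.** Protocol 12.4.1.4 has laboratory tests listed, 12.4.3.2 flags out-of-range values in the listings, and 9.3.3.2.4 requires clinically relevant changes to be reported as adverse events. A reader might infer that thyroid data are lost or that a signal would be hidden; the documents do not support that.
- **The protocol is itself uneven.** Its safety paragraph (12.4.3) names only hematologic, biochemical and urinalysis parameters, and 12.4.3.2 never mentions thyroid by name. The duty to summarise it comes from general wording. That wording has no exception, though, and it is the section specific to laboratory data.
- **Thyroid could be filed under chemistry.** It could, but the protocol keeps the two apart and the SAP does not say so. The SAP's open-ended allowance for other safety analyses (10.2) permits a thyroid table without specifying one.
- **No formal comparison is lost.** Protocol 12.4.3 plans none for safety endpoints, and SAP 10.0 calls any such comparison post hoc.
- **Redaction.** Parts of the protocol are blacked out, but the test table and footnote d read as complete, and the visit procedures spell out the panels.

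On repeats, a reader might infer that the two SAP sentences contradict each other and produce opposite shift categories. They can mostly be read together and part only in the narrow cases above. Even there, the expected change is from abnormal to normal, not from low to high.

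**Conclusion.** The mismatch is certain: SAP 10.3 and the protocol cannot both stand on the fourth laboratory panel. Followed literally, the SAP produces one empty table and no by-arm thyroid summary or shift table. About 180 post-baseline values stay in listings only, on the assumption of about 60 subjects with a Visit 8/ET sample. A reader might quote 360 as the on-treatment figure, but half of those are Screening values.

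The effect is limited to descriptive safety tables. No efficacy result, hypothesis test or data collection changes. It should be corrected before database lock because safety is the protocol's objective and the data already exist. The repeat rule and oral temperature are minor points; the repeat rule touches only subjects with retests, or with a Visit 8 sample after Day 42.

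**What to change.** - In both places in SAP 10.3, replace *Coagulation Profile* with *Thyroid Panel* (TSH, free T3, free T4), covering summary statistics, change from baseline and shift tables. If coagulation testing was intended, correct the protocol instead. Thyroid would still have to be added to the SAP while the protocol collects it.
- Minor: state in SAP 10.3 that when a Visit 8 or ET sample is repeated, the first evaluation at that visit is used and retests are listed. Say also that ET samples on any day, and Visit 8 samples within Day 42 ± 2, count as end of study. The window must not be applied to ET samples, or early discontinuers would drop out of the shift table.
- Minor: add oral temperature to SAP 10.4.

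The cost is SAP wording, one relabelled table shell and one added vital sign. No new data are needed unless coagulation is added to the protocol.
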